## 10.9 Interim and Final Analyses and Reporting

Interim analyses will include descriptive summaries of patient characteristics and vernakalant IV administration and dosing, as well as frequencies and cumulative incidence of HOIs and SAEs following administration. Two-sided 95% confidence intervals around rates of HOIs will be computed.

## **Vernakalant IV Sterile Concentrate Prospective Safety Registry Study**

Sponsor Protocol Identifier: 6621-049-00

3 August 2016

---

A final study report summarising patient characteristics and details of vernakalant IV administration and dosing, administration of concomitant treatment modalities, frequencies and cumulative incidence of HOIs and SAEs over the full study period, as well as effectiveness and frequencies of non-serious AEs will be prepared.

Full explanation of study methods, results, and discussion and interpretation will be included with interim and final study reports.

## **11 MANAGEMENT OF THE STUDY**

The Sponsor has contracted with Outcome Sciences LLC (formerly operating as Outcome Sciences Inc.) together with its affiliate Quintiles Switzerland Sarl, a CRO specialising in registries and observational post market studies. The CRO will design and manage the study with input, review and approval by the Sponsor. Each participating site will receive appropriate training, which describes all processes that the physician or representative must understand. The training will outline all processes required for enrolling patients, providing follow-up data on enrolled patients, maintaining study documents or files, reporting of medically significant HOIs and SAEs, and closing the study. All site staff who participate in enrolling patients and collecting or entering data for the study will be required to undergo appropriate training.

### **11.1 Data Entry**

Data for the study will be collected using a secure web-based electronic data capture (EDC) system (Outcome System®). Data captured during or shortly following the administration of vernakalant IV are entered into the eCRF by the physician or delegated site staff in a timely manner.

### **11.2 Source Documents**

The physician should maintain source documents for each patient enrolled in the study. Source documents include patient charts, doctors' notes, study-specific supplementation data collection forms, ECG tracings (including conversion to sinus rhythm ECGs within 90 minutes of vernakalant IV treatment), lab results slips, supportive documentation of all HOIs and SAEs, and worksheets designed to collect the data to be entered in the CRF and will be kept as part of the patients' medical records. Baseline ECG tracings recorded as part of standard of care during the index hospitalization and prior to vernakalant administration and ECGs corresponding to arrhythmic HOIs and SAEs during the follow-up period may also be requested.

Data recorded into the e-CRF should also be downloaded and stored on local computers at the site. Should this not be possible sites will print a date-stamped version of the completed CRF for each patient to be signed by the study physician and stored in files at the site.

## **Vernakalant IV Sterile Concentrate Prospective Safety Registry Study**

Sponsor Protocol Identifier: 6621-049-00

3 August 2016

---

### **11.3 File Retention and Archiving**

The physician and trained staff at the study sites will maintain a record of each enrolled patient. Physicians will be instructed on source documentation that must be available to substantiate patient identification, eligibility and participation, proper informed consent procedures, dates of data collection, adequate reporting and follow-up of medically significant HOIs and SAEs, concomitant medication, and drug administration. Specific items required as source documents will be reviewed with the physician before the study.

Physicians must retain all study records required by the Sponsor and by the applicable regulations a secure and safe facility. The physician must notify the Sponsor or its representative before disposal of any study records, including the medical records of study participants, and must notify the sponsor of any change in the location, disposition, or custody of the study files. In the event that archiving of study records is not possible at the site, the physician will be instructed to notify the Sponsor or its representative.

### **11.4 Quality Assurance**

The study database will be housed at the CRO in a physically and logically secure computer system maintained by the CRO in accordance with company written security policies. The system meets approved established standards for the security of health information and is validated. The system also meets the standards of the International Committee on Harmonisation (ICH) guideline E6R1 regarding electronic study data handling and is available for audit upon request. Each step of the data capture procedures and the handling of data, as well as the eventual study report may be subject to independent quality assurance audits. The CRO, the Sponsor, and the Competent Authorities may conduct site audits at any time during or after the study to ensure the validity and integrity of the data.

### **11.5 Data Management**

A data management plan will be created and will describe all functions, processes, and specifications for data collection, cleaning and validation. The eCRFs will include programmable edits to obtain immediate feedback if data are missing, out of range, illogical or potentially erroneous. Concurrent manual data review will be performed based on parameters dictated by the plan. Ad hoc queries will be generated within the EDC system and followed up for resolution.

### **11.6 Monitoring**

Monitoring will be performed by a CRO clinical research associate (CRA). During the site initiation visit, the CRA will provide training on the conduct of the study to the participating physician and all site staff involved in the study. All monitoring procedures and the frequency of monitoring visits will be described in a monitoring plan. The CRA will closeout each site after

## **Vernakalant IV Sterile Concentrate Prospective Safety Registry Study**

Sponsor Protocol Identifier: 6621-049-00

3 August 2016

---

the last patient's final follow-up assessment is completed and all e-CRF data has been entered and all outstanding monitoring issues have been resolved or addressed. In the case where a site is closed before completion of the study, the CRA will close out the site but will maintain contact with the physician regarding the study status and in case follow-up information is required.

### **11.7 External Safety Review Committee (SRC)**

The Sponsor will assemble a team of external advisors for an SRC and will employ a charter for the SRC developed jointly by the Sponsor and the CRO. The SRC will consist of three members (single Chairperson and two members) based in Europe with expert knowledge in AF and therapeutic modalities for cardioversion. Two experts will have clinical experience in treatment of AF while the third member will be an applied epidemiologist or statistician with experience in the design and execution of observational safety study studies.

The Sponsor will contact each advisor to review the requirements and expectations of participation in the SRC. Regularly-scheduled meetings of the SRC (teleconference, webex, or face-to-face) will be convened prior to the start of study enrolment and at least annually thereafter, to review interim and final reports of safety data and monitor overall study progress. Specifically, the SRC will be responsible for (1) review of individual patient listings of serious adverse event (SAE) reports and aggregated data in the form of predefined tables and study result reports; (2) periodic assessment of subject accrual rate and study status; (3) evaluation on an *ad hoc* basis of any urgent safety issue identified by the Sponsor, CRO or the SRC; (4) document and communicate in writing all SRC activities to Sponsor, and (5) adjudication of Health Outcomes of Interest (HOIs)/Serious Adverse Events (SAEs).

Source documentation routinely collected for the study which may include ECG tracings corresponding to arrhythmic events if performed as part of standard of care will also be provided to the SRC for review of individual HOIs and SAEs.

### **11.8 Changes to Protocol**

Changes to the protocol will be documented in written protocol amendments. Major (substantial, significant) amendments will usually require submission to the competent authorities and to the relevant ECs for approval or favourable opinion. In such cases, the amendment will be implemented only after approval or favourable opinion has been obtained. Minor (non-substantial) protocol amendments, including administrative changes, will be filed by the Sponsor and/or the CRO and at each participating site. They will be submitted to the relevant EC or to competent authorities where required by pertinent regulations.

As noted below in Section 12.1 regarding Informed Consent, any amendment that could have an impact on the patient's agreement to participate in the study (e.g., changing the nature of the data collected) requires re-consent of the patient prior to implementation, except if a waiver of consent has been approved by the relevant EC or competent authorities.

**Vernakalant IV Sterile Concentrate Prospective Safety Registry Study**

Sponsor Protocol Identifier: 6621-049-00

3 August 2016

---

**11.9 Publication Policy**

The Sponsor will post a study design synopsis on [www.clinicaltrials.gov](http://www.clinicaltrials.gov) within 60 days after the study protocol is approved by the CHMP, and will post final study results within 12 months after the last patient is enrolled in the study. In addition, publication may also include any or all of the following: posting of a synopsis online abstract and/or presentation at a scientific conference, or publication of a full manuscript.

In the event that the key design elements from the protocol, including methods, and main results of the study are made public through publication in peer-reviewed journals, it is anticipated that one central draft manuscript will be prepared with input from key investigators and leadership from the CRO and the Sponsor.

Authorship credit should be based on 1) substantial contributions to conception and design, or acquisition of data, or analysis and interpretation of data; 2) drafting the article or revising it critically for important intellectual content; and 3) final approval of the version to be published. Authors should meet conditions 1, 2, and 3. Significant contributions to study execution may also be taken into account to determine authorship, provided that contributions have also been made to all three of the preceding authorship criteria. Although publication planning may begin before conducting the study, final decisions on authorship and the order of authors' names will be made based on participation and actual contributions to the study and writing, as discussed above. The first author is responsible to defend the integrity of the data, method(s) of data analysis, and the scientific content of the manuscript.

The Sponsor must have the opportunity to review and comment on all proposed abstracts, manuscripts, or presentations regarding this study 60 days prior to submission for publication/presentation. During this 60 day period, Sponsor may respond with any requested revisions. Any information identified by the Sponsor as confidential must be deleted prior to submission. If reasonably requested, Sponsor will take reasonable steps to expedite the review process to meet publication deadlines. Submission may be made upon notification by Sponsor that such review has been completed and after information identified by Sponsor as confidential is deleted. Sponsor also has the right to publish the results of this study. Publications and authorship will be guided by the Uniform Requirements for Manuscripts Submitted to Biomedical Journals: Writing and Editing for Biomedical Publication of the International Committee of Medical Journals Editors, updated April 2010.

## **Vernakalant IV Sterile Concentrate Prospective Safety Registry Study**

Sponsor Protocol Identifier: 6621-049-00

3 August 2016

---

## **12 ETHICAL AND REGULATORY CONSIDERATIONS**

This is an observational study which sets forth to observe the safety outcomes of patients having been administered vernakalant IV. To ensure the quality and integrity of pharmacoepidemiologic research, the study will be conducted in compliance with all applicable national and local regulations and guidelines, accepted standards of Good Clinical Practice, the Guidelines for Good Pharmacoepidemiology Practices (GPP), [Ref. 5.4: 437] the ethical principles that have their origin in the Declaration of Helsinki [Ref. 5.4: 440], EudraLex Volume 9A, Part 1, Chapter I.7. [Ref. 5.4: 435] and the Guideline on good pharmacovigilance practices (GVP), Module VIII [Ref. 5.4: 436].

### **12.1 Patient Information and Informed Consent/Accent**

It is expected that a prerequisite for a patient's participation in the study is informed consent from the patient or a legal representative; however the possibility of conducting this study with a waiver of consent will be explored in each country.

The physician will obtain written informed consent as needed from each patient or a legal representative if incapacitated prior to enrolment and data collection. The physician, or delegated personnel, is required to provide patient or legal representative with the informed consent in their local language. The informed consent document contains adequate information on risks of study participation, in this case, limited to communication of personal identifiers and health information. This informed consent document will be approved by the appropriate EC as will any revisions to the document. Each patient or legal representative will be provided a copy of the informed consent document and the original will be maintained at the site. Confirmation of signed informed consent documents obtained as required will be one of the primary activities performed by the CRA during onsite monitoring as defined in the monitoring plan.

### **12.2 Patient Identification and Privacy**

By signing the protocol, the clinical site and/or physician commit to complying with all related applicable local laws and regulations as well as any applicable EU regulations, such as the *EU Data Protection Act*.

Each patient will be unambiguously identified by a code, which allows the identification of all the data reported for each patient. The code will be an 8-digit number resulting from the combination of the site number and the patient number. The first four digits represent the site and the last four digits represent the patient. Should a patient be withdrawn from the study, his or her unique identification number will not be reallocated.

**Vernakalant IV Sterile Concentrate Prospective Safety Registry Study**

Sponsor Protocol Identifier: 6621-049-00

3 August 2016

---

**12.3 Independent Ethics Committees**

Patient enrolment will not start at any site before the Sponsor has obtained written confirmation of a favourable opinion/approval from the concerned EC. At certain sites it may be deemed unnecessary for an EC to review an observational study. If this is the case, confirmatory documentation will be maintained on file with both the Sponsor and the clinical site.

Before implementation of any substantial changes to the protocol, protocol amendments will also be submitted to the relevant EC in a manner consistent with local regulations. Pertinent safety information will be submitted to the relevant ECs during the course of the study in accordance with local regulations and requirements.

## Vernakalant IV Sterile Concentrate Prospective Safety Registry Study

Sponsor Protocol Identifier: 6621-049-00

3 August 2016

---

**Post-Authorisation Safety Study (PASS) Study**

**Annex to Protocol for German Sites – 29 October 2015**

**Purpose of the Annex**

To clarify selection of patients at German sites.

**Inclusion Criteria**

The inclusion criteria for enrolment are:

1. Patients treated independently from this study with vernakalant IV in accordance with the SmPC, for rapid conversion of recent onset atrial fibrillation to sinus rhythm in adults:
  - For non-surgery patients: atrial fibrillation  $\leq$  7 days duration
  - For post-cardiac surgery patients: atrial fibrillation  $\leq$  3 days duration
2. Subjects and/or legal guardians willing to provide informed consent and/or informed assent according to local regulations

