## **Vernakalant IV Sterile Concentrate Prospective Safety Registry Study**

Sponsor Protocol Identifier: 6621-049-00

3 August 2016

2. In order to investigate the potential risk of overdose and medication error, describe vernakalant IV administration/dosing by summarising patient body weight, total dose with each intravenous (IV) infusion, and length of time for each IV infusion.
3. To evaluate the effectiveness of the risk minimisation activities by:
  - Describing the appropriateness of selection of patients for treatment with vernakalant IV, monitoring of patients during and after vernakalant IV administration, and use of anti-arrhythmics before and after vernakalant IV, as consistent with the label and risk minimization activities (Pre-Infusion Checklist and healthcare provider (HCP) educational card)
  - Monitoring for the occurrence and incidence of serious adverse events (SAEs) and HOIs to review with the EU Regulatory Agency with respect to risk minimization activities

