## **6 SELECTION OF PATIENTS**

### **6.1 Inclusion Criteria**

The inclusion criteria for enrolment are:

- Patients treated with vernakalant IV, independently of this study

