**Vernakalant IV Sterile Concentrate Prospective Safety Registry Study**

Sponsor Protocol Identifier: 6621-049-00

3 August 2016

---

retrospective) and unadjusted incidence and 95% confidence interval will be reported. In addition, results will also be reported separately by method of enrolment. Results will be calculated for the combined endpoint of (1) bradycardia requiring electrical pacing (temporary or permanent) or (2) any other serious adverse events reports involving bradycardia, and for each endpoint separately.

Numbers and rates of HOIs will also be presented according to time intervals since start of vernakalant IV administration, i.e., 0 to less than 2 hours, 2 to less than 4 hours, and 4 hours to a maximum of 24 hours. Characteristics of patients with HOIs, which may include prior medical history, presenting conditions, medication use, dosing/administration of vernakalant IV, and concomitant therapies, and assessment of relatedness as provided by the investigator will be summarised in a listing of individual HOI events in study reports. Case narratives will also be provided for each HOI.

The primary analysis for HOI incidence is the 0-2 hour post infusion timepoint. Given the lower expected sample size, vernakalant's mode of action and the non-interventional nature of the study design, the 2-4 and 4-24 hour post infusion timepoints are considered secondary and tertiary analyses, respectively.

It is anticipated that rates of HOIs may be somewhat higher in this real-world study setting compared to rates observed in the vernakalant clinical trial program due to the selective patient entry criteria of these randomized clinical trials. Likewise, comparisons to the published literature are not planned and would prove difficult due to differences in case definitions for each specific HOI and variability of reported follow-up periods from administration of a given study drug or intervention to time of the event. However, the frequency of HOIs will be carefully monitored by the Sponsor, the CRO, and the independent Safety Review Committee throughout the duration of the registry study.

***Primary Objective 2: In order to investigate the potential risk of overdose and medication error, describe vernakalant IV administration/dosing by summarising patient body weight, total dose with each IV infusion, and length of time for each IV infusion.***

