### **10.7 Sample Size**

The study will enroll 2,000 patients across participating EU countries. The target sample size was selected in order to have adequate statistical precision as expressed by a 2-sided, 95% confidence limit around the expected incidence rate for each HOI for sample sizes of 500, 1,000 1,500; and 2,000 patients. The incidence of each HOI during the first 24 hours post-vernakalant IV administration as defined in Section 5.0 and 10.2 above among patients randomised to receive vernakalant IV in the pooled phase II/III clinical trial database (n=889, including the AVRO Study) ranged from 0% to 0.22% for each HOI.

Table 1 shows the margins of error, defined as the distance from the expected proportion to the upper limit of the confidence interval as shown in the table, and confidence limits of the two-sided 95% confidence intervals with sample size of 500, 1,000, 1,500, and 2,000, respectively. For example, if the expected proportion of significant hypotension is 0.003 and the sample size is 1,500, the margin of error is 0.004, and the lower and upper bounds of the two-sided 95% confidence interval will be 0.001 and 0.007, respectively. The calculation of the confidence intervals was performed using the Clopper-Pearson exact method [Ref. 5.4: 406] and PASS software (2008, Kaysville, Utah).

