**Exclusion Criteria**

The exclusion criteria for enrolment are:

1. Patients with the following contraindications:
  - Hypersensitivity to the active substance or to any of the excipients.
  - Patients with severe aortic stenosis, patients with systolic blood pressure  $< 100$  mm Hg, and patients with heart failure class NYHA III and NYHA IV.
  - Patients with prolonged QT at baseline (uncorrected  $> 440$  msec), or severe bradycardia, sinus node dysfunction or second degree and third degree heart block in the absence of a pacemaker.
  - Use of intravenous rhythm control antiarrhythmics (class I and class III) within 4 hours prior to, as well as in the first 4 hours after, BRINAVESS™ administration.
  - Acute coronary syndrome (including myocardial infarction) within the last 30 days.
2. Enrolment in an investigational drug or device clinical trial in the 30 days prior to study enrolment. Participation in another non-interventional drug or device study or registry is permitted.

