4.3 Subgroup Analysis

The tables relating to patient selection (i.e., demographics, presenting conditions, and medical history) and vernakalant dosing and administration will be repeated for each country. Country-specific tables will include:

- **Table 1.2** Use of Pre-Infusion Checklist Prior to Vernakalant IV
- **Table 1.3** Receipt of Healthcare Provider (HCP) Educational Card, by Site
- **Table 4.1** Patient Demographics
- **Table 5** Other Baseline Presenting Conditions and Medical History
- **Table 9.1** Vernakalant IV Administration and Dosing (Overall)
- **Table 9.2** Vernakalant IV Administration and Dosing (Prospective Patients)
- **Table 9.3** Vernakalant IV Administration and Dosing (Retrospective Patients)
- **Table 10** Patient Age and Therapeutic Indication for Use in Accordance with the Vernakalant IV Summary of Product Characteristics
- **Table 11** Contraindications for Use in Accordance with the Vernakalant IV Summary of Product Characteristics

Rates of HOIs will not be reported by country or other specified subgroups as individual events are expected to be rare, and stratification of event rates will yield statistically unstable results.

Secondary analysis of rates of HOIs may be conducted for subgroups of patients with certain medical characteristics if the sample size is sufficient to allow for reasonably precise point estimates of HOI incidence (in general, 500 patients or more). Regardless, a description of each patient with an SAE or HOI will be given in narrative form.

A pre-specified secondary analysis of the effectiveness of vernakalant will be restricted to a subgroup of patients who receive vernakalant IV in accordance with the Summary of Product Characteristics (SmPC). Specifically, the following patients will be **excluded** from the pre-specified subgroup analysis:

- Patients not administered vernakalant IV in accordance to SmPC in terms of adult indication (age < 18 years of age), therapeutic indication (indication other than conversion of atrial fibrillation), duration of atrial fibrillation (atrial fibrillation > 7 days for non-surgery patients and > 3 days for post-cardiac surgery patients).

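### Patients enrolled under the German annex are on-label by entry criterion, so pooling them lowers the Objective 3 patient-selection percentages, and the SAP neither counts nor marks them

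*Protocol*

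**What the plan says.** Protocol 6.1 sets the general entry criterion as "Patients treated with vernakalant IV, independently of this study", plus consent. The only exclusion in 6.2 is recent participation in an investigational trial. No label condition applies.

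The Annex to Protocol for German Sites, dated 29 October 2015, narrows this. Its inclusion criterion is "Patients treated independently from this study with vernakalant IV in accordance with the SmPC", with AF-duration limits for non-surgery and post-cardiac-surgery adults. Its exclusion list covers the label contraindications, including "Patients with severe aortic stenosis, patients with systolic blood pressure" below a threshold, advanced heart failure, prolonged QT, conduction disease without a pacemaker, recent acute coronary syndrome, and intravenous class I/III anti-arrhythmics in the four hours before or after dosing. The annex says its purpose is to clarify selection. It does not say which criteria applied to German patients enrolled earlier.

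Part of Primary Objective 3 is "Describing the appropriateness of selection of patients for treatment with vernakalant IV". SAP 5.8 measures this in Table 10 (age, indication, AF duration) and Table 11 (contraindications), each with Analysis Set, prospective and retrospective columns. SAP 4.3 repeats both tables by country. SAP 4.2 limits the analysis set to patients who meet the eligibility criteria. The SAP does not mention the annex.

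For the safety outcomes, SAP 4.3 states: "Rates of HOIs will not be reported by country or other specified subgroups".

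**The concern.** The appropriateness of selection cannot be measured in patients admitted because their selection was appropriate. A German site working under the annex may treat a contraindicated patient but cannot enrol that patient, so its rows in Tables 10 and 11 read about 0% whatever its practice is. When these patients share a denominator with patients enrolled under the unrestricted criteria, the pooled off-label and contraindication percentages move towards compliance. Those percentages are part of the evidence on risk minimisation that goes to the regulator.

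A reader of the country tables would see German zeros with nothing to separate good practice from an entry rule. The non-participation reasons in SAP 5.1.1 have no entry for treatment outside the label, so the number turned away on that ground is not shown either.

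The same selection enters the pooled HOI incidence. Protocol 10.2 expects real-world HOI rates above trial rates "due to the selective patient entry criteria of these randomized clinical trials". The annex brings comparable criteria back for one country.

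**Working it through.** **1. Do the annex criteria match the outcome rows?** Table 10 reports adult age, indication, and AF duration against the 7-day and 3-day limits; the annex requires all of these. Table 11 reports systolic pressure below 100 mmHg, MI/ACS within 30 days, severe aortic stenosis, severe bradycardia, prolonged QT, sinus node dysfunction, heart block, NYHA III/IV, and intravenous class I/III anti-arrhythmics within four hours before or after dosing. Each row has a counterpart in the annex exclusions. SAP 4.2 would also drop a patient enrolled in breach of the annex, whereas Protocol 10.1 would keep that patient. Dosing, infusion time, monitoring and checklist use are not listed as annex criteria.

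**2. The plan's own precision figure.** Protocol 10.7 says: "if the expected proportion of significant hypotension is 0.003 and the sample size is 1,500, the margin of error is 0.004". The Clopper-Pearson interval with 0.003 × 1,500 = 4.5 events is 0.0009 to 0.0073, a margin of 0.0043. This agrees with the plan after rounding.

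**3. Dilution of a selection percentage.** Let p be the true percentage among patients not under the annex, and w the annex share of the column. Annex patients contribute zero, so the pooled percentage = p(1 − w). The documents give neither p nor w; p = 10% is assumed below for illustration.

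**4. Range of w for the 2,000-patient Analysis Set.** Appendix I plans 810 further patients, so 1,190 were already enrolled. Germany is to add 55, all prospective.
- *Only the 55 planned patients:* 55/2,000 = 2.75%; 10% reads 9.7%.
- *From the annex date:* about 9.2 months to the protocol date of 3 August 2016, at 0.4 × 8 sites = 3.2 per month, gives about 29 more. (55 + 29)/2,000 = 4.2%; 10% reads 9.6%.
- *Annex applied throughout, past enrolment in proportion to vials:* German vials for 2011–2015 are 4,410 of 13,451 (Austria 4,110, Denmark 555, Spain 1,414, Sweden 2,962, Germany 4,410), or 32.8%. 0.328 × 1,190 ≈ 390, and (390 + 55)/2,000 = 22%; 10% reads 7.8%.

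**5. Prospective column.** No German patient is among the 435 planned retrospective patients, so the dilution falls only on the prospective column. If all 1,190 earlier patients were prospective (an assumption), that column holds 2,000 − 435 = 1,565. The three shares become 55/1,565 = 3.5%, 84/1,565 = 5.4% and 445/1,565 = 28%, and 10% reads 9.6%, 9.5% and 7.2%. The comparison of enrolment methods is therefore affected too.

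**6. HOI incidence.** Let RR be the HOI risk ratio of off-label to on-label patients. The relative fall in the pooled incidence = w × p(RR − 1)/[1 + p(RR − 1)]. With p = 10% and RR from 2 to 5 (both assumed), the fraction multiplying w runs from 0.1/1.1 = 0.091 to 0.4/1.4 = 0.286. The fall is 0.4–1.2% at w = 4.2% and 2.0–6.4% at w = 22%. At an incidence of 0.003, a 6.4% fall is about 0.0002. The exact interval at N = 2,000 is 0.0011 to 0.0065.

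**The case against.** The strongest reply is that little is lost. Tables 10 and 11 are planned by country, so anyone can set the German rows aside. HOIs can be separated too: Listing 1a carries country and contraindications, and Table 3 gives numbers by country. Protocol 6.3.2 already requires a screening log with reasons, and the Figure 1 footnote cites ineligibility as a data source. The annex also came late, four years after the planned launch, with only 55 German patients still to come.

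Much of this stands, and it limits the size of the point. It does not answer it. The country split is not the annex split: German patients enrolled before the annex may have met the unrestricted criteria, and no planned output tells the two groups apart. No table says why the zeros arise, the pooled percentages remain uncorrected, and the log has no specific reason for off-label treatment.

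Three stronger readings are tempting, and the documents do not support them.
- A reader might take w as 33% (the vial share) or 40% (the country cap). The vial share could describe at most the first 1,190 patients. A 40% share means 800 German patients, so 800 − 55 = 745 of those 1,190 (63%) would have to be German.
- A reader might infer that HOI incidence is materially understated, citing the trial rates in heart-failure patients (clinically meaningful hypotension 2.9% against 1.2% overall; ventricular arrhythmia 2.2% against 0.6%). Those rates cover all heart failure, while the annex excludes only NYHA III/IV. They also count SAEs and discontinuations rather than the study's HOIs, which ran at 0–0.22%. They suggest a direction, not a size.
- A reader might conclude that all German sites should be dropped from Objective 3. That would discard any genuine off-label use recorded before the annex, along with monitoring and checklist data that the annex does not list as entry criteria.

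**Conclusion.** The point holds for the patient-selection part of Primary Objective 3. Under the annex, the entry criteria and the outcome are the same items, and the SAP pools the result without comment. The bias is towards compliance and equals the annex share of the column. In the Analysis Set that is about 2.75–4% in relative terms if the annex applied only from its date. It is about 22% if the annex applied throughout and past enrolment followed vial sales. The documents do not settle which, and the 10% used for illustration is an assumption. The uncertainty about w is itself a reason to report it.

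For HOI incidence the effect is probably downward, is not quantified by the documents, and is likely small relative to the exact interval. It justifies a sensitivity column, not a change to the primary estimate.

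**What to change.** In SAP 5.6, 5.8 and Tables 10 and 11, state the annex, its effective date and the number of patients enrolled under its criteria. Report the selection percentages with and without those patients, and name the version without them as the Objective 3 selection estimate. Footnote the annex-restricted cells, in the country tables as well, as *excluded by entry criteria*.

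Split by annex status, not by country. Keep German patients not enrolled under the annex, and all German dosing, monitoring and checklist data, in the analysis.

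Add one sensitivity column excluding annex-restricted patients to Tables 8.1.1, 8.2.1 and 8.3.1. Add one reason, *outside SmPC / contraindicated (German annex)*, to the non-participation reasons in SAP 5.1.1 and Figure 1.

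The cost is SAP wording, extra columns and one reason code on an existing log, with no new patients. The selection denominator becomes somewhat smaller and the compliance figures slightly less favourable. Precision in the HOI sensitivity column barely changes if only the 55 planned patients are affected: at 0.003 and N = 2,000 − 55 = 1,945 the exact interval is 0.0011 to 0.0066, against 0.0011 to 0.0065 at 2,000.
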